8.2.6 Protocol Deviations

Any deviations from the procedure outlined in this Protocol should be recorded as Protocol Deviations in the eCRF (see Section 11.8 for further detail).

8.3 Adverse Events

For this study, all SAEs, all Device and/or Procedure-Related AEs and all Device Deficiencies must be reported for all Subjects.

8.3.1 Adverse Event Determination

Adverse Event determination will be done by the Principal Investigator, or appropriate designee. The Investigator will record the nature, severity, treatment and outcome of the AE, and will determine the level of association to the device and/or the study procedure.

8.3.2 Adverse Events Not Required to be Reported to the Sponsor

There are particular immediate post-operative events that are changes from the baseline condition of the Subject but are expected events resulting from surgery, in general. For the purposes of this protocol these are referred to as Non-Reportable Adverse Events and are listed in Exhibit A and are not included in the product IFU. If these events occur, they should be recorded in the Subject's medical record, but these should NOT be reported as AEs in the eCRF or to the Sponsor.

8.3.3 Adverse Event Definitions

The definitions of various type of Adverse Events are provided below:

Table 8-3 Adverse Event Definitions

Term	Details
Adverse Event (AE)	Any untoward medical occurrence, unintended disease or injury, or untoward clinical signs (including abnormal laboratory findings) in subjects, users or other persons, whether or not related to a medical device.
	Note: This definition includes a) events that are anticipated as well as unanticipated events. b) events related to the medical device under study and c) events related to the procedures involved. See Table 8.5 for definitions of expectedness and Section 8.3.4 for AE reporting requirements.
	Adverse Event is synonymous with complication or medical event.
Serious Adverse Event (SAE)	An Adverse Event that: leads to death, leads to a serious deterioration in the health of the subject, that either resulted in:
	o a life-threatening illness or injury,
	a permanent impairment of a body structure or a body function,
	o in-patient hospitalization or prolongation of existing hospitalization,
	 medical or surgical intervention to prevent life-threatening illness or injury or permanent impairment to body structure or a body function,
	leads to fetal distress, fetal death or a congenital abnormality or birth defect.
	Note: Planned hospitalization for a pre-existing condition, or a procedure required by the CIP, without serious deterioration in health, is not considered a serious adverse event.

Term	Details
Adverse	An adverse event related to the use of the medical device under study.
Device Effect	
(ADE)	Note: This definition includes adverse events resulting from insufficient or
	inadequate instructions for use, deployment, implantation, installation or operation,
	or any malfunction of the medical device under study. This definition includes any
	event resulting from use error or from intentional misuse of the medical device under
	study.
Unanticipated	An adverse device effect which by its nature, incidence, severity or outcome has not
Adverse	been previously identified in the current version of the risk analysis report.
Device Effect	
(UADE)	Note: Event will also not be listed in the Instructions for Use.
Serious	An adverse event related to the use of a medical device that has resulted in any of
Adverse	the consequences characteristic of a serious adverse event.
Device Effect	
(SADE)	
Unanticipated	A serious adverse device effect which by its nature, incidence, severity or outcome
Serious	has not been identified in the current version of the risk analysis . This definition
Adverse	includes any event resulting from insufficiencies or inadequacies in the instructions
Device Effect	for use or the deployment of the device. This definition includes any event that is a
(USADE)	result of a user error.
	Note: Event will also not be listed in the Instructions for Use.
Expected/	A serious adverse device effect which by its nature, incidence, severity or outcome
Anticipated	has previously been identified in the current version of the risk analysis report.
Serious	
Adverse	Note: Event will also be listed in the Instructions for Use.
Device Effect	
(ASADE)	
Device	Inadequacy of a medical device related to its identity, quality, durability, reliability,
Deficiency	safety or performance, such as malfunction, misuse, use error or inadequacy in
(DD)	information supplied by the manufacturer.
Awareness	The day, month and year that the study site becomes aware of information from any
(Date of AE	source that reasonably suggests that an Adverse Event has occurred.
Awareness)	
	Note: This date may or may not correspond to the date of onset. The date of
	awareness is critical to reporting timelines (see Section 8.3.4).

8.3.3.1 Determination of Anticipated / Unanticipated

For the purpose of this protocol, the term "expected" will be synonymous with the term "anticipated" and "unexpected" will be synonymous with "unanticipated".

The PI is responsible for determining whether an AE is anticipated or unanticipated. This determination is based on whether the severity, type and frequency of the AE is consistent with the Instructions for Use (IFU) in the opinion of the PI. Note that since TKA is a routine elective procedure, the majority of adverse events are anticipated and included in the IFU.

DSJ_2019_05, Rev D (FINAL) 24 August 2022

When a PI classifies an AE as unanticipated, the Sponsor will also review and classify anticipated/unanticipated based on the reported event and in consideration of the IFU and internal risk reports. In the event that the Sponsor has a different opinion on anticipated/unanticipated, a query will be generated. When there is a discrepancy between the site and the Sponsor, both opinions will be recorded and reported as required to the relevant IRB/EC/Regulatory Authority.

8.3.3.2 Determination of AE Severity

Severity refers to the intensity of the symptoms experienced by the study subject and can be used with any event, without regard to whether or not the AE is classified as Serious. Definitions are provided below.

Table 8-4: Definitions of Severity of AEs

Term	Description
Severe	The intensity of the symptoms is severe and poorly tolerated, requiring intervention, and
Symptoms	significantly affect activities of daily life; or place the Subject at immediate risk or harm.
Moderate	The intensity of the symptoms is moderate. Intervention is either noninvasive or not
Symptoms	indicated. Activities of daily living can be sustained.
Mild Symptoms	The intensity of the symptoms is mild, transient or asymptomatic. Intervention is not
	indicated. Clinical or diagnostic observations only and no impairment of normal activity.

8.3.3.3 Determination of Relationship to Device and/or Procedure

The determination whether the AE is related to the device and/or procedure will be based upon whether a causal relationship between the device or procedure and the AE is at least a reasonable possibility, i.e., the relationship cannot be ruled out. A causal relationship cannot be ruled out if, in the medical judgment of the Investigator, the effect follows a reasonable temporal association with the use of the device and/or is confirmed by the improvement of the effect upon discontinuation of the clinical use of the device, and/or the effect is not reasonably explained by the Subject's clinical state. The Investigator must document all AEs which occur in the Subject's medical record along with the determination of relationship to device and/or procedure to ensure it is clearly documented which AEs will or will not be reported to the Sponsor based on this relationship. Definitions for Device and Procedure Relatedness of AEs are provided below.

Table 8-5: Definitions of Device Relatedness and Procedure Relatedness for AEs

Caused By	Term	Description
	Not Related	Relationship to the study device can be excluded.
Study Device	Possible	The relationship with the use of the study device is weak but cannot be ruled out completely.
Study Device	Probable	The relationship with the use of the study device seems relevant and/or the event cannot be reasonably explained by another cause, but additional information may be obtained.

DSJ_2019_05, Rev D (FINAL) 24 August 2022

Caused By	Term	Description
	Causal Relationship	The event is associated with the study device beyond reasonable doubt.
Study Procedure	Not Related	Relationship to the procedure can be excluded
	Possible	The relationship with the study procedure is weak but cannot be ruled out completely.
	Probable	The relationship with the study procedure seems relevant and/or the event cannot be reasonably explained by another cause, but additional information may be obtained.
	Causal Relationship	The event is associated with the study procedure beyond reasonable doubt.

8.3.3.4 Outcome

The outcome of each AE must be assessed according to the classifications below.

In the event of a previously reported AE which has worsened significantly, the original AE is to be listed as Recovered/Resolved and a new AE reported for the worsened AE. The worsened AE will then be linked to the original AE in the eCRF.

Table 8-6: Adverse Event Outcome Classifications

Classification	Definition
Recovered/Resolved	Subject fully recovered with no observable residual effects
Recovered/Resolved with sequelae	Subject recovered with observable residual effects
Recovering/Resolving	Subject's condition improved, but residual effects remain
Not recovered/Not resolved	AE is ongoing without changes in the overall condition
Fatal	Subject died as a result of the AE (whether or not the AE is related to the device or procedure)
Unknown	Information is not available

8.3.4 Adverse Event Reporting Guidelines

8.3.4.1 AE Reporting by Site to Sponsor

Subjects should be encouraged to report AEs spontaneously or in response to general, non-directed questioning (e.g. "How has your health been since your last visit?"). The Subject may volunteer information relating to AEs at any time during the Study. If an event occurs at an outside institution, the Investigator should attempt to obtain, if possible, required AE information.

All SAEs and all Device and/or Procedure-Related AEs must be reported to the Sponsor, regardless of classification, severity or outcome. The Investigator is responsible for ensuring that all protocol reportable

DSJ_2019_05, Rev D (FINAL) 24 August 2022

AEs observed by the Investigator (or designee), or reported by the Subject, that occur from the intraoperative time frame through to the end of the Study (either study completion or withdrawal of consent) are properly assessed, recorded and reported. All protocol reportable AEs must be documented in the study Subject's medical records (source documents) and reported in the database on the Adverse Event eCRFs. All AEs will be monitored until they are adequately resolved or explained. When a Subject ends participation in the study (either through study completion or consent withdrawal) an AE must be designated either as "resolved" (end date must be provided), or as "ongoing."

Table 8-7: Adverse Event Reporting Requirements to Sponsor

Type of Adverse Event	Reporting Requirements
SAEs (including SADEs, USADEs and	Report to Sponsor by completing an AE eCRF or by direct
ASADEs)	contact to Sponsor (i.e. via phone or e-mail) immediately
All Implant Device Deficiencies	upon awareness of event but no later than 72 hours.
(including those that potentially could	
have led to an AE/SAE*)	If related to an Implant/Instrument Device Deficiency, also
	complete a Device Deficiency eCRF as soon as possible but
	no later than 72 hours.
AE (Device and Procedure Related,	Report to Sponsor by completing an AE eCRF or by direct
including ADEs and UADEs). See Table	contact to Sponsor (i.e. via phone or e-mail) immediately
8.5 for further definition of AE	upon awareness of event but no later than 72 hours.
relatedness	
AEs related to a Device Deficiency	Report to Sponsor immediately upon awareness of event
	but no later than 72hrs, in line with Device Deficiency
	reporting requirement above.
All other AEs not listed above	Report to Sponsor within 2 weeks of awareness.

^{*} if a) suitable action had not been taken, or b) intervention had not been made or, c) if circumstances had been less fortunate.

Pre-existing medical conditions or symptoms reported prior to the surgical event are to be recorded as part of the medical history and not to be recorded/reported as AEs⁵. The only exception would be in the event there is an exacerbation of a pre-existing medical condition or symptom(s) in the post-operative time frame, then an AE must be reported.

^{*}NOTE: Not meeting the above reporting timelines to the Sponsor will result in a Protocol Deviation.

⁵ An example could be pre-existing contralateral knee osteoarthritis with a planned TKA intervention after the index knee surgery.

[figure not shown]

Figure 8.2 AE Reporting Flowchart

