8.3.4.3 Regulatory Reporting Requirements

All reported protocol-required AEs will be reviewed by DePuy Synthes and reported if applicable to the appropriate regulatory bodies.

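### The protocol is inconsistent on whether non-serious adverse events unrelated to device or procedure go to the Sponsor, so their tabulated rates would be too low at any site that withholds them

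*Combined protocol and SAP*

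**What the plan says.** Several passages of the protocol bear on which adverse events (AEs) a site sends to the Sponsor.

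- **Section 8.3:** "all SAEs, all Device and/or Procedure-Related AEs and all Device Deficiencies must be reported for all Subjects".
- **Section 8.3.3.3:** the investigator documents every AE and its relatedness in the medical record, so that it is clear "which AEs will or will not be reported to the Sponsor based on this relationship".
- **Section 8.3.4.1, prose:** "All SAEs and all Device and/or Procedure-Related AEs must be reported to the Sponsor, regardless of classification, severity or outcome". The same paragraph continues "All protocol reportable AEs must be documented", using a term that the protocol does not define.
- **Section 8.3.4.3:** "All reported protocol-required AEs will be reviewed", a second undefined term.
- **Section 12.3, item j:** monitors check reporting of serious AEs, device- and procedure-related AEs, and device deficiencies.
- **Table 8-7, last row:** "All other AEs not listed above" are due within 2 weeks of awareness. A note after the table adds: "Not meeting the above reporting timelines to the Sponsor will result in a Protocol Deviation".
- **Section 8.3.2:** under the heading "Adverse Events Not Required to be Reported to the Sponsor", the text deals with the Exhibit A events (expected post-operative events).

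On the analysis side, type and frequency of AEs is a secondary endpoint (Section 6.2, Table 6-1). Section 9.8.4.2 tabulates AEs by system organ class and preferred term for all subjects in the Safety set, giving the proportion of subjects with each event and an exact binomial 95% interval.

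**The concern.** A coordinator with a non-serious AE judged unrelated to device and procedure finds two answers. Section 8.3.3.3 implies that the event may stay in the medical record because of its relationship. Table 8-7 requires it within 2 weeks and makes a missed timeline a Protocol Deviation.

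If sites resolve this differently, the Section 9.8.4.2 denominators include subjects whose events of this kind were never sent. The affected rates, and any totals that include them, would be biased downward, and the exact intervals would not reflect that. Item j of Section 12.3 does not name this class, so that check would not reveal the gap; the general compliance check in item a might. Section 3.1 says the data will support CE mark registration, so readers of the tables need to know what the tables cover.

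**Working it through.** **1. Which events are in dispute.** The earlier rows of Table 8-7 cover serious AEs, implant device deficiencies, device- and procedure-related AEs, and AEs related to a device deficiency. What remains for the last row is non-serious AEs unrelated to device or procedure. Sections 8.3 and 8.3.4.1 require serious AEs whatever their relationship. So if 8.3.3.3 leaves anything out because of relationship, it is this same class.

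**2. Can the texts be read together?**

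- *The last row means other reportable AEs.* Every class named as reportable in 8.3 and in the 8.3.4.1 prose already has its own row, so the last row would be empty.
- *The related row covers only events related to both device and procedure, leaving the last row for events related to one.* That row expressly includes adverse device effects, which Table 8-3 defines by relation to the device alone, and the prose uses and/or.
- *Section 8.3.3.3 refers to the Exhibit A events.* Those are excluded as part of the normal post-operative course, not because of relatedness.

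None of these removes the conflict. Sections 8.3, 8.3.4.1 (prose) and 12.3 j lean towards the narrow scope but do not say *only*. Section 8.3.2 leans towards the table but does not say that Exhibit A is the only exclusion.

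**3. Size.** The plan gives no rate for these events and no figure to reproduce. What follows is illustration only.

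Inputs from Section 7: at least 600 subjects, at most 25 sites, at most 50 subjects per site. Assumptions: 600 subjects, equal incidence at all sites, and silent sites that report none of these events.

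Relative reduction per silent site = site size / 600:

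- 600/25 = 24 subjects: 24/600 = 4.0%
- 50 subjects (site maximum): 50/600 = 8.3%

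A smaller site lowers the rate by less.

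**4. Effect on the interval.** Take 25 equal sites of 24, with k silent. For true incidence p, the observed count X is Binomial(24 × (25 − k), p), still divided by 600. Coverage is the probability that X falls among the counts whose exact (Clopper-Pearson) 95% interval out of 600 contains p. For p = 5% those counts are 20 to 41; for p = 10%, 46 to 75; for p = 2%, 6 to 19; for p = 20%, 101 to 139.

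| Assumed true incidence | k = 0 (600 reporting) | k = 1 (576) | k = 5 (480) |
|---|---|---|---|
| 2% | 96.0% | 96.0% | 91.6% |
| 5% | 96.1% | 95.8% | 82.6% |
| 10% | 95.9% | 94.9% | 64.2% |
| 20% | 95.4% | 93.2% | 30.1% |

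With k = 5, the expected rate falls by 120/600 = 20% in relative terms: from 5% to 4.0%, or from 10% to 8.0%. One silent site hardly matters for the less common events. Five matter more as the event becomes more common.

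**The case against.** The best defence is that the protocol says where the governing rule sits. The AE definition in Table 8-3 sends the reader to Section 8.3.4 for reporting requirements, and Table 8-7 there has an express catch-all with a deviation attached. The 8.3.3.3 wording is a purpose clause inside a documentation duty. It names no excluded class, and taken alone as the rule it would also drop unrelated serious AEs, which other sections require. Figure 8.2, the reporting flowchart, is not visible in the text reviewed and may show the intended rule.

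Much of this stands. A reader might infer that 8.3.3.3 is an explicit exclusion; it is not, and a careful site would probably follow the table. But the prose directly above the table speaks of reportable AEs without defining them, and the sentence that comes nearest to a definition names the narrow set. A flowchart could show intent, but it would not make the two texts agree.

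A reader might also argue that the effect is negligible: with five silent sites and a true rate of 5%, the expected result is 24/600 = 4.0% (exact 95% interval 2.6% to 5.9%), which still contains 5%. That treats the expected count as if it were certain. Once sampling variation is allowed for, coverage in that case is about 83%.

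**Conclusion.** The conflict is real, lies in current text, and is minor. For non-serious AEs unrelated to device or procedure, 8.3.3.3 and the last row of Table 8-7 cannot both be followed. A site that withholds such events lowers their tabulated rates and also incurs Protocol Deviations.

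The wording mismatch is certain; under-counting is conditional. The documents do not show how any site reports, so a reader who inferred that the AE rates are in fact too low would go beyond them. The illustrative figures (4.0% to 8.3% relative per silent site; coverage of about 83% or 64% with five of 25 silent at 5% or 10% incidence) rest on assumed incidences, equal incidence across sites and complete silence at the sites concerned.

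Nor do the documents support inferring a wider safety or efficacy problem. The tabulation is descriptive in a single-arm study. Rates of serious and related AEs, device deficiencies, survivorship and the KOOS primary endpoint do not depend on the disputed class.

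**What to change.** Bring Sections 8.3, 8.3.3.3, the 8.3.4.1 prose, Table 8-7 with its note, and 12.3 j to one reporting scope chosen by the sponsor. Define the terms used for reportable AEs in 8.3.4.1 and for required AEs in 8.3.4.3 to match, and check Figure 8.2 against the result.

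In Section 9.8.4.2, state which AEs the tables cover:

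- **Narrow scope chosen:** limit rates and intervals to serious AEs and device- and/or procedure-related AEs, and only list any other AEs received.
- **All-AE scope chosen:** keep the all-AE table, note that capture of non-serious unrelated AEs may be incomplete before the amendment, and show serious and related AEs separately. Section 8.3.1 already has the investigator determine relatedness.

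The cost is a wording amendment with IRB/EC approval before implementation (Section 12.1), a site memo and slightly more tabulation. Sites enter more data only under the wider scope. Sample size, visits and the primary analysis do not change.

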8.3.4.2 Institutional Review Board (IRB) / Ethics Committee (EC) Reporting

In any instances of Serious Adverse Events, Serious Adverse Device Effects, Unanticipated Adverse Device Effects, Unanticipated Serious Adverse Device Effect, the Clinical Investigator is responsible for informing the IRB/EC in accordance with their local procedures. The Clinical Investigator should institute appropriate therapeutic and follow-up measures in accordance with good medical practice and record them in the subject's source documentation.

8.3.4.3 Regulatory Reporting Requirements

All reported protocol-required AEs will be reviewed by DePuy Synthes and reported if applicable to the appropriate regulatory bodies.

8.3.5 Safety Oversight

Safety oversight will be conducted by the study Safety Lead. Study data will be reviewed periodically throughout the Study in order to promptly identify new issues or trends which may have an impact on the conduct of the study and/or Subject safety.

8.4 Discontinuation of Subject Participation

Study participation may be discontinued through screen failure, not receiving the tibial base implant, revision of the femoral and/or tibial component(s), withdrawal of consent, or death. Table 8-8 describes how data will be captured on Subjects that are discontinued prior to receiving the study device while Table 8-9 describes post-op withdrawal scenarios. In all cases, once a subject is enrolled (per Figure 8-1), if they discontinue study participation, the Subject Completion/Discontinuation eCRF must then be completed.

8.4.1 Enrolment Replacement Rules

Since Subjects are enrolled at the time of consent, any Subject that is withdrawn pre-operatively and or does not receive the study required tibial / femoral implants will be replaced with a subsequent Subject. Overall, the number of Subjects who receive a TKA procedure with the study required tibial / femoral components across all sites must meet the minimum sample size of 300 patients per configuration (CR Femoral with CR or MS Tibial Insert or PS Femoral with PS Tibial Insert) and up to 300 cementless patellae (across both configurations). Intra-operative withdrawals will also be replaced with a subsequent Subject and will be assessed to understand reasons why the implant was not appropriate for use in that subset of Subjects.

Table 8-8: Data Collection for Enrolled Subjects Who are Subsequently Found to be Pre-operative and Intra-operative Screen Failures

Screen Failure Type	Screening/ Enrolment Log?	Data submitted on eCRF?	Enrolled Subject?	Example	Action
Pre-operative screen failure (discovered post-consent but pre-op)	Yes	Yes	Yes	Subject withdrew consent or the Subject no longer met inclusion/ exclusion criteria.	 Complete Subject Completion/Discontinuation eCRF Recruit an additional subject
Pre-operative screen failure (Discovered post-op)	Yes	Yes	Yes	Age criteria not met	Keep as Subject – continue to follow as per Safety population Complete Protocol Deviation eCRF
Intra-operative screen failure	Yes	Yes	Yes	Did not implant ATTUNE Cementless Tibial / Femoral device	Complete Subject Completion/Discontinuation eCRF Recruit an additional subject

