8.2.3 Operative Management

The preparation of the subject for a total knee arthroplasty should follow the Surgeon's standard of care. Once the patient is ready for the first incision the surgical workflow should follow the ATTUNE® Knee System Surgical Technique Featuring the ATTUNE® Fixed Bearing Porous Knee for the devices to be implanted (hereinafter known as "Surgical Technique"). The Surgical Technique will be provided to all study Sites prior to the start of the study. Deviation from the relevant Surgical Technique must be reported as a Protocol Deviation.

Table 8.2: Protocol Requirements During Surgery

Surgical Process Detail	Protocol Instructions
Instrumentation	Surgeons are permitted to use any instrumentation specified in the current Surgical Technique for the region in which the surgery is completed.
Femur and Tibia Treatment	ATTUNE Cementless Cruciate Retaining (CR) or Posterior Stabilized (PS) Femoral Implants are to be used in combination with the ATTUNE Cementless Fixed Bearing (FB) Tibial Base implant and appropriate ATTUNE Tibial Insert.

NOTE: If a subject is enrolled in the clinical study prior to implementation of this protocol amendment and receives the ATTUNE Medial Stabilized Tibial Insert as part of the investigator's standard of care, that subject will remain in the study, but must be reconsented with the updated IRB approved ICF which includes the Medial Stabilized insert. A Protocol Deviation must be completed for use of a non-study device with the ATTUNE Cementless Tibia. Once this protocol is IRB approved, no further Protocol Deviations are required for use of the Medial Stabilized Insert from the date of IRB approval forward as long as the subject signs the consent including the Medial Stabilized Tibial Insert as an option.

In this study, bone cement must not be used with the ATTUNE Cementless Femoral or Tibial Base components. If bone cement is used on either of these components, a Protocol Deviation CRF must be recorded and the patient will continue in the study as part of the Safety Population. However, if the site is located in the US and uses DePuy Synthes Antibiotic Impregnated Bone Cement (off-label use), a Protocol Deviation CRF must be recorded and the patient will be discontinued from the study (Study Completion/Discontinuation eCRF). The subject will be replaced with another enrolled subject.

Patellar Treatment

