9.6.1 ITT Analysis Set

The ITT analysis set consists of all subjects who are consented and enrolled into the study. Subjects in the ITT analysis set who do not undergo surgery to implant the ATTUNE Cementless FB tibial base will be withdrawn from the study without any further data collection. The purpose of this analysis set is to provide accountability for these subjects who do not receive the ATTUNE Cementless FB tibial base system. There are no other analyses which are planned for this dataset.

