9.6.2 Safety Analysis Set

The Safety analysis set consists of all ITT subjects who undergo surgery to implant the ATTUNE Cementless FB tibial base. Subjects who withdraw from the study prior to surgery will not be included in the Safety analysis set.

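### Section 8.4.1 and Table 8-8 can be read as ending follow-up of a knee that has the study tibial base but not the study femoral component, whereas 8.4 and 9.6 turn on the tibial base alone

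*Combined protocol and SAP*

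**What the plan says.** Two sets of passages apply different tests.

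**Both components.** Section 8.4.1 says that a subject who "does not receive the study required tibial / femoral implants will be replaced with a subsequent Subject". Its next sentence sets the count per configuration: "the number of Subjects who receive a TKA procedure with the study required tibial / femoral components across all sites must meet the minimum sample size". In Table 8-8 the example of an intra-operative screen failure is "Did not implant ATTUNE Cementless Tibial / Femoral device". The actions listed are a Completion/Discontinuation form and an additional recruit, with no instruction to follow the subject. The row above it, for a screen failure discovered after surgery, does tell the site to keep following the subject in the Safety population.

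**Tibial base alone.** Section 8.4 opens: "Study participation may be discontinued through screen failure, not receiving the tibial base implant". It adds that "Table 8-8 describes how data will be captured on Subjects that are discontinued prior to receiving the study device". Section 9.6.1 says that ITT subjects "who do not undergo surgery to implant the ATTUNE Cementless FB tibial base will be withdrawn from the study without any further data collection". Section 9.6.2 states: "The Safety analysis set consists of all ITT subjects who undergo surgery to implant the ATTUNE Cementless FB tibial base". The only device criterion in 9.6.3 (Per Protocol) is also the tibial base.

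**Related provisions.** Sections 9.6 and 9.8.4.2 run the adverse event and Kaplan-Meier analyses on the Safety set. Table 6-1 limits the adverse event endpoint to subjects who are not screen failures. Section 8.5 excludes data after withdrawal from the analysis. On cementing a cementless femoral or tibial component, Table 8.2 says: "If bone cement is used on either of these components, a Protocol Deviation CRF must be recorded and the patient will continue in the study".

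**The concern.** Take a knee in which the surgeon implants the cementless fixed bearing tibial base but uses a femoral component from outside the study. Under 8.4.1 and Table 8-8 this subject lacks one of the required implants, so the site would complete the discontinuation form and recruit a replacement. Under 8.4 and 9.6.1 nothing triggers withdrawal, and 9.6.2 puts the subject in the Safety set.

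Section 3.1 says the study is to show the safety and effectiveness of the tibial base and that the data will support CE marking. Survivorship of the base is a secondary endpoint. A base that is implanted and then not followed is missing from the evidence the study exists to collect, and that follow-up cannot be recovered later. Section 8.4.1 itself plans to ask why the implant was not appropriate in intra-operative withdrawals, so these are selected cases and a difference in risk is plausible. The documents do not show that there is one.

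**Working it through.** **1. Does missing either component trigger the rule?** The wording joins tibial and femoral with a slash. Suppose it means that neither was implanted. Then a subject with the femoral component but no tibial base would escape 8.4.1 and Table 8-8, although 8.4 and 9.6.1 withdraw exactly that subject. The same phrase also defines who counts toward 300 per configuration, where both components are needed. Missing either one is therefore the more natural reading. It is not the only one available to a site, because 8.4 confines Table 8-8 to subjects discontinued before receiving the study device.

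**2. Where does the subject with the base but not the study femoral component fall?**

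| Provision | Test | Result for this subject |
|---|---|---|
| 8.4.1 and Table 8-8 | tibial / femoral implants | discontinued and replaced |
| 8.4, reason for discontinuation | tibial base | not discontinued |
| 8.4, scope of Table 8-8 | before receiving the study device | arguably outside the table |
| 8.5 and Table 8-9 | implanted, later withdrawn | definition fits if the site withdraws the subject; no row names this case |
| 9.6.1 withdrawal rule | tibial base | not withdrawn |
| 9.6.2 Safety set | tibial base | in |
| Table 6-1 adverse event population | not a screen failure | out, if classed as a screen failure |
| 9.6 and 9.8.4.2 adverse event analysis | whole Safety set | in |

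**3. Plan's own figures.** None concerns this rule. The primary sample size was reproduced to see whether it is affected. Inputs from 9.4 and 9.7: null 85%, alternative 91%, one-sided alpha 0.05, power 80%, attrition 15%.

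n = [(1.645 × √(0.85 × 0.15) + 0.842 × √(0.91 × 0.09)) / 0.06]² = 190.5, so 191. Then 191 / 0.85 = 224.7, so 225.

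Both match the plan. Nothing in the rule enters this calculation.

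**4. Number of knees (assumed share).** The documents give no rate.
- 1%, 2% and 3% of 600 = 6, 12 and 18 knees.
- If 600 is instead the number retained after replacement, the count is 600 × f / (1 − f): 6, 12 and 19 for the same shares.

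**5. Adverse event proportions.** If the denominator is the whole Safety set and the unfollowed knees contribute no events, the proportion is multiplied by (1 − f). An illustrative 10% then reads 10% × 0.99 = 9.9% to 10% × 0.97 = 9.7%. Under the Table 6-1 population these knees leave the denominator and there is no dilution.

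**6. Survivorship.** Censoring at about day 0 removes a knee from the risk set and does not in itself lower the revision estimate. Assume 5-year revision of 2% in 600 retained knees and risk r in x unfollowed knees. The rate over all implanted bases is (600 × 0.02 + x × r) / (600 + x), against a reported 2.00%.
- r = 2%: 2.00% for any x, so no bias.
- r = 10%, x = 6: (12 + 0.6) / 606 = 2.08%.
- r = 10%, x = 12: (12 + 1.2) / 612 = 2.16%.
- r = 10%, x = 19: (12 + 1.9) / 619 = 2.25%.
- For shares of 0.5% (x = 3) and 5% (x = 32), r = 10% gives 2.04% and 2.41%.

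**The case against.** The strongest reply is that the parent section governs. Section 8.4 names only the tibial base, confines Table 8-8 to subjects who never received the study device, and agrees with 9.6.1. Section 8.4.1 itself speaks only of replacement and counting, and the discontinuation form appears only in the table. On that view the subject is never stopped. This stands as far as it goes: the fault is a contradiction between passages, not a settled rule that implanted bases go unfollowed. A reader might infer the settled rule, but the documents do not support it. They also do not exclude it, and a site completing forms from Table 8-8 would end follow-up.

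Four further points stand.
- A reader might infer that adverse event proportions are diluted. That depends on the unresolved conflict between Table 6-1 and 9.6.
- A reader might infer that survivorship is biased. That needs unequal risk, which the documents do not show.
- A reader might infer that Table 8.2 always keeps recipients of the base in follow-up. It does not: use of the sponsor's antibiotic-impregnated cement leads to discontinuation and replacement, with off-label use given as the reason. A cemented study femoral component is also still a study component, unlike a femoral component outside the construct in Table 10-1.
- These subjects are not wholly ignored. Section 8.4.1 assesses reasons for intra-operative withdrawal, and 8.3.4.1 collects reportable events from the intra-operative period. Neither provides later follow-up.

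**Conclusion.** The point holds as an inconsistency with a practical consequence. The natural reading of 8.4.1 and Table 8-8 discontinues a recipient of the tibial base whom 8.4 and 9.6.1 do not withdraw and whom 9.6.2 keeps in the Safety set. If sites follow Table 8-8, that base has no follow-up after surgery.

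The effect is probably small: 6 to 18 knees at an assumed 1% to 3% of 600. Any dilution of adverse event proportions is about 1% to 3% in relative terms, and only with the whole Safety set as denominator. At the same shares the assumed risks of 2% and 10% put 5-year revision at 2.08% to 2.25% against a reported 2.00%; with equal risks there is no bias. All of these shares and risks are assumptions. The primary sample size does not change. The amendment is worth making because it is cheap and uncollected follow-up cannot be recovered, but the point does not threaten the primary conclusion.

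**What to change.** Reconcile Table 6-1, 8.4, 8.4.1 with Table 8-8, 8.5 and 9.6.1 to 9.6.3 so that study data collection matches the Safety set:

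1. Limit the intra-operative discontinuation row of Table 8-8 to subjects in whom the tibial base was not implanted.
2. For a subject with the base but not the study femoral component, record a Protocol Deviation and continue Safety follow-up for adverse events and revision. Make 8.5 consistent with this. Still allow the subject to be replaced for the count of 300 per configuration.
3. State in 9.6.3 whether Per Protocol requires the study femoral component. As written, a retained subject with one post-operative evaluation and no meaningful eligibility deviation would qualify and could enter the primary analysis.
4. Align the adverse event population in Table 6-1 with 9.6 and 9.8.4.2.
5. State how removal of a non-study femoral component counts in the tibial base survivorship analysis. Section 9.8.4.2 uses the 8.6 definition of revision, which includes removal of a femoral component.

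The cost is amendment wording, follow-up of a few more subjects who have already consented, and a slightly more mixed set of constructs in the Safety set. The change concerns data collection only and does not alter patient care.
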